9.5.2 Laboratory Tests

Standard of care laboratory assessments will be undertaken at Screening as well as various time points during treatment and at follow up.

Urine samples should be collected at home ideally as the first void of the morning on the visit day using a sample collection kit provided by the site. Caregivers will be provided instruction on procedures for

collecting the samples to reduce contamination.

- Complete Blood Count with Differential (Visits 1, 3, 5, 7, 9, 11, 13, 16, 17): Hemoglobin (Hb), hematocrit (Hct), red cell count (RBC), white blood cell count (WBC), mean cell volume (MCV), mean cell hemoglobin (MCH), mean cell hemoglobin concentration (MCHC), platelets (PLT), red cell distribution width (RDW-CV), and leukocyte count (neutrophils, lymphocytes, monocytes, eosinophils, and basophils). If abnormalities are seen, additional tests may be conducted as deemed necessary by the Investigator and Medical Monitor and as described below in the clinical management plan in Sections 9.5.2.1 and 9.5.2.3.
- Coagulation (Visits 1, 3, 5, 7, 9, 11, 13, 16, 17): prothrombin time test, International normalized ratio (INR), activated partial thromboplastin (aPTT). If abnormalities are seen, additional tests may be conducted as deemed necessary by the Investigator and Medical Monitor and as described below in the clinical management plan in Sections 9.5.2.1 and 9.5.2.3.
- Comprehensive Metabolic Profile (All Visits except Visit 2): amylase, sodium, glucose, potassium, blood urea nitrogen (BUN), enzymatic creatinine, BUN/creatinine ratio, estimated glomerular filtration rate (eGFR), bicarbonate, chloride, total calcium, phosphorus, magnesium, bilirubin (direct and indirect), creatine kinase, alkaline phosphatase (ALP), aspartate transaminase (AST), alanine amino transferase (ALT), gamma-glutamyl transferase (GGT), total protein, albumin, total cholesterol, and random triglycerides. If abnormalities are seen, additional tests may be conducted as deemed necessary by the Investigator and/or Medical Monitor and as described below in the clinical management plan in Sections 9.5.2.1 and 9.5.2.3.
 - o eGFR is calculated using the modified Bedside Schwartz formula: eGFR=(0.413*height)/creatinine mg/dL
 - This formula will be used for all participants including those who may age up to 18 years old during the study
- **Urinalysis** (All Visits except Visit 2): with microscopic analysis, glucose, bilirubin, ketones, specific gravity, blood, pH, protein, albumin, urobilinogen, nitrite, and leucocyte esterase. If abnormalities are seen on microscopy, additional tests for culture, sensitivity and protein analysis may be conducted as deemed necessary by the Investigator and/or Medical Monitor, and as described below in the clinical management plan in Section 9.5.2.2.
- Urine will also be tested at Screening, for drugs of abuse, i.e., stimulants (e.g., amphetamine, methamphetamine, methylenedioxymethamphetamine [MDMA], cocaine), hallucinogens (e.g., phencyclidine), narcotics/analgesics/ opiates (e.g., codeine, morphine, methadone, propoxyphene), depressants/sedatives/hypnotics (e.g., barbiturates).
- **TSH, Free T3, Free T4** (Visits 1, 16): free triiodothyronine (T₃), free thyroxine (T₄), thyroid stimulating hormone (TSH).
- Glycosylated hemoglobin (HbA1c) (Visits 1, 16)
- Rapid test for SARS-CoV-2 (Visits, 1, 3, 16). The site may use any test with same day results approved for use for children and adolescents in the US.

[figure not shown]
• Serum Pregnancy Test (Visits 1, 9, 16): Females who have reached menarche will have a serum pregnancy test (β-HCG) at Screening, Visit 9 (Week 6) and at Visit 16 (Week 13, EOT).

A central laboratory will be used for the safety sample analysis. Details on sample collection, handling and shipment are outlined in the Laboratory Manual. The laboratory range reference list is also provided in the Laboratory Manual. Abnormal or out of range values should be reviewed by the Investigator who should make a determination if the values are clinically significant. The laboratory reference list designates normal ranges (for age and sex as applicable), and critical alerts for all blood and urine labs. If abnormal results are observed in any of the above tests, additional tests may be conducted via the central laboratory or the site's local laboratory as deemed appropriate by the Investigator and/or the Medical Monitor.

It is preferable that repeat labs are done through the central laboratory. If not feasible, repeat labs may be collected at the site's laboratory or a local laboratory. Repeat labs should be ordered stat. If repeat labs are done through the central lab, a deidentified copy of the report must be provided in the participant's study file. The reference values for the laboratory test for that lab must also be obtained and filed in the study files.

9.5.3 Blood sample for biomarkers and stool sample for microbiome

Blood and stool samples will be collected at Visits 1 (Screening), 3 (Baseline), and 16 (Week 13, EOT) or upon early termination for analysis of biomarkers and gut microbiome. The analysis will be detailed in a separate analysis plan but will not include DNA sequencing.

9.5.4 Medical/Clinical History

A complete medical history will be performed at all Screening and Baseline visits (Visits 1, 2, 3) to document all current medical conditions, and previous major medical events and conditions. For participants who may receive their on-going care at the study site, summary documents from the medical record (such as clinician's summaries) should be available as source documentation of major medical conditions or events (e.g., surgeries) within the last two years. For participants who are not a part of the clinical site's practice, the study team should request families obtain summary medical records from their primary care provider (if available, or another qualified healthcare professional as determined by the Investigator) in preparation of the Screening visit. At each in-clinic and combined remote visit (Visits 4, 5, 7, 9, 11, 13, 16 and 17), a current clinical history will be conducted by the Investigator or appropriately credentialed delegate. This will include review of any changes in urine voids or oral intake.

9.5.5 Physical and Neurological Exam

A physical and neurological exam including a complete, standard review of systems will be undertaken by a physician (or appropriately credentialed delegate) at all in-clinic visits. The physical exam procedures will include the following organ systems: Head, ears, eyes, nose, and throat; Skin; Cardiovascular; Respiratory; Gastrointestinal; Genitourinary (as appropriate or indicated); Musculoskeletal; Allergies. The exam will include an assessment for signs of bladder or kidney pathology including an exam of the abdomen and both flanks, looking for signs of discomfort or distress. Assessment of edema will also be performed. Exam may include suprapubic exam (bladder palpation) to assess for urinary retention if decreased urine output is noted.

A standard neurological exam will be undertaken at all in-clinic visits to include an evaluation of mental status, cranial nerves, motor exam, sensory exam, cerebellar (coordination, gait), reflexes.

A modified version of the physical and neurological exam will be performed by a physician (or appropriately credentialed delegate) via telemedicine at the remote visits [Visits 7 (Week 4), 11 (Week 8), 13 (Week 10), and 17 (Week 15)] based on guidance documents provided to the Investigator. The modified version of the neurological exam will follow recommendations for conducting telemedicine exams from the Child Neurology Society. Additionally, as part of the in-home visit, the nurse will conduct a targeted physical exam including assessment of general appearance, an abdominal and a costovertebral angle tenderness exam, assessment for signs of cystitis, and an assessment of edema. Exam may include suprapubic exam (bladder palpation) to assess for urinary retention if decreased urine output is noted. These are done at Visits 4 (Week 1), 6 (Week 3), 7 (Week 4), 8 (Week 5), 10 (Week 7), 11 (Week 8), 12 (Week 9), 13 (Week 10), 14 (Week 11), 15 (Week 12), and 17 (Week 15).

9.5.8 12-lead ECG and Stopping Criteria for Prolonged QT

Formal assessments of QTcF and cardiac irregularities will be done at Screening (Visit 1), Baseline (Visit 3), Visit 5 (Week 2), Visit 9 (Week 6), EOT (Week 13, Visit 16) and Follow Up (Visit 17). At each designated visit, a continuous ECG of at least 50 seconds will be obtained. Ideally, the participant should be supine for at least 5 minutes before the first ECG reading is taken. If this is not possible, this should be documented in the source and the EDC.

If the clinician determines that an ECG is invalid due poor quality or major artefact during data collection, the ECG should be deleted and reassessed. If the clinician is uncertain if the ECG can be read, duplicate ECGs may be submitted to the central reader. The central reader will read and interpret all readable ECGs

submitted. The clinician will be queried to adjudicate which ECG should be considered the final read and entered into the database.

ECGs will be sent via secure transmission and read by a qualified central reader. The results from the reports from the central reader and any alert flags should be reviewed by the Investigator who will determine if the values are clinically significant and sign the report. Results will be assessed against the ECG screening criteria for QTcF at the Screening visit and against the QTcF stopping criteria throughout the study.

Investigational Medicinal Product must be discontinued at any time during the study in the event that a post-enrollment QTcF duration of ≥ 500 ms confirmed by a repeat continuous ECG, or a clinically significant increase of ≥ 60 ms (confirmed by a repeat continuous ECG) compared to the average QTcF interval at Baseline (Visit 3, before dosing) is observed.

9.5.9 Battery of Pitt-Hopkins Syndrome Assessment Instruments

The battery of PTHS specific measures will evaluate symptom change in clinically meaningful and functionally impactful symptom domains for individuals with PTHS including communication, cognition, motor function, maladaptive behavior, adaptive behaviors, sleep, seizures, breathing and GI issues (see Section 6.3.2). The selection of outcome measures for this study reflects the insights from the published literature, and expert clinical advice.

All assessments will be administered in a standardized manner by trained practitioners. To the extent possible, all efforts should be made to maintain the same caregiver informant or investigator rater (as applicable) across visits for a single participant. If in extenuating circumstances (such as severe illness), the caregiver is unable to complete the rating for a visit, another appropriate rater can be designated to complete the assessment for that visit. This should be documented in the source and the EDC. The site staff should ensure the alternative rater has appropriate knowledge of the participant to complete the rating and is informed of the instructions for completing the assessments.

Caregivers will complete most assessments via an online portal. Paper versions of assessments will also be used and may be made available for online versions in the case of difficulty accessing the electronic portal. These assessments should be completed the day of the visit or no earlier than the day before the visit. No assessments can be conducted until informed consent has been given by the caregiver or legally authorized representative. Also, training for the caregivers on all caregiver completed assessments must be completed before the caregiver rater may complete the assessments.

Overall symptom severity and functional level will be assessed using the following tools:

9.5.9.1 Clinical Global Impression of Severity (CGI-S)

Clinical Global Impression of Severity assessments will be done at Screening (Visit 1), Baseline (Visit 3), Week 6 (Visit 9), EOT (Week 13, Visit 16), and Follow-up (Week 15, Visit 17). The Clinical Global Impression - Severity scale (CGI-S)³⁶ is a 7-point scale that requires the Investigator to rate the severity of the individual's overall illness at the time of assessment, relative to the Investigator's past experience with participants who have the same diagnosis.³⁶ Considering total clinical experience, a participant is assessed on severity of illness at the time of rating: 1, normal, not at all impaired; 2, borderline, slightly impaired; 3, mildly impaired; 4, moderately impaired; 5, markedly impaired; 6, severely impaired or 7, among the most extremely impaired ill. Following best practice for neurodevelopmental disorders, the CGI-S will be evaluated using PTHS-specific scoring anchors. The clinicians will provide an overall global severity rating and a severity rating for each of seven domains: language/communication, fine motor functioning/self-help, social initiation/social avoidance, challenging behavior, ambulation/gross motor,

gastrointestinal issues, and autonomic/breathing abnormalities. The clinician rater should assess the participant's current state taking into consideration observations at the visit and symptoms within the last week. To ensure that interpretation of the scoring rubric is normalized among the raters, clinicians administering the CGI-S will be required to complete scoring calibration training.

9.5.9.2 Clinical Global Impression of Improvement (CGI-I)

Clinical Global Impression of Improvement assessments will be made at Visit 9 (Week 6), EOT (Week 13, Visit 16), and Follow-up (Week 15, Visit 17). The CGI-I scale³⁶ requires the Investigator to rate how much the participant's illness has improved or worsened relative to a baseline state. A 7-point scale is used with the following values: 1, very much improved; 2, much improved; 3, minimally improved; 4, no change; 5, minimally worse; 6, much worse; 7, very much worse. The CGI-I will be evaluated using PTHS-specific scoring anchors. The clinicians will provide an overall global improvement rating and an improvement rating for each of seven domains: language/communication, social initiation/social avoidance, fine motor functioning/self-help challenging behavior, ambulation/gross motor, gastrointestinal issues, and autonomic/breathing abnormalities. The clinician should assess the participant's current state taking into consideration observations at the visit and symptoms within the last week. The rating of change is compared with status at Baseline (Visit 3). To ensure that interpretation of the scoring rubric is normalized among the raters, clinicians administering the CGI-I will be required to complete scoring calibration training.

9.5.9.3 Bayley Scales of Infant Development v4 (BSID4) or Stanford-Binet Intelligence Scales v5 (SB5)

The Stanford-Binet Intelligence Scales version 5 (SB5) assessment will be done at Screening (Visit 1) and EOT (Week 13, Visit 16). SB5 is validated for ages 2 to 85+ and measures both verbal and nonverbal intellectual and cognitive abilities through a set of 10 subtests. The General cognitive ability is reported as a full-scale intellectual quotient score (FSIQ). Cognitive ability in five categories are reported in the index scores: fluid reasoning (FR), knowledge (KN), quantitative reasoning (QR), visual-spatial processing (VS), and working memory (WM). Non-verbal (NVIQ) and verbal intelligence quotients (VIQ) are also calculated. Scoring of index scores and IQ will be calculated using the z-deviation method for intellectual disability.

The Bayley Scales of Infant Development version 4 (BSID-4) is conducted for participants who cannot achieve a basal score on SB5or for whom the SB5 is developmentally inappropriate. ³⁹ Assessment will be done at Screening (Visit 1) and End of Treatment (Week 13, Visit 16). The Bayley is a norm-referenced developmental assessment validated for ages 16 days to 42 months. It assesses cognitive ability, motor skills, and behavior and provides standardized scores in five domains: Cognitive, Language, Motor, Social-Emotional, and Adaptive Behavior. Scale scores, age equivalents and growth scale values (GSVs) can also be calculated for the scale subtests: cognition (CG), receptive communication (RC), expressive communication (EC), fine motor (FM), and gross motor (GM). Scaled scores and age equivalents can be calculated for the social emotional (SE) subscale. The Adaptive Behavior subscale will not be collected in this study. The Early Learning Composite score and scaled scores are calculated for children 42 months and younger. Raw scores, age equivalents, and growth scale values are calculated for all participants.

If the SB-5 or the Bayley had previously been administered for the participant within 3 months of Screening, the scores from that administration may be used if it meets the following criteria: 1) assessment was administered by site personnel, or another study site; 2) the site has access to all the scores required to be entered in the EDC; 3) the site has permission to share the scores from the previously administered assessment to the study EDC. Assessments done by the school or other clinics

are not acceptable. Only scores from SB-5 and the Bayley are acceptable; cognitive scores from other assessments cannot be entered in the EDC in lieu of the SB-5 or the Bayley.

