6.3.2.1 Secondary Endpoints

Within-participant changes will be assessed from the Baseline period to End of Treatment (EOT) using the following measures:

Overall Improvement:

- PTHS-specific Clinical Global Impression Scale–Improvement (CGI-I) Overall Improvement Score; clinician-assessed
- PTHS-specific Clinical Global Impression Scale—Domain Improvement Scores; clinicianassessed
- Caregiver Global Impression of Change Scores; caregiver-assessed

PTHS Symptom Severity:

- Clinical Global Impression Scale—Severity (CGI-S)—Overall Severity Score; clinicianassessed
- Clinical Global Impression Scale-Severity (CGI-S)-Domain Scores; clinician-assessed
- Caregiver Top 3 Concerns Likert Scale Scores; caregiver-assessed

Communication

- MacArthur-Bates Communicative Development Inventory (MB-CDI) Scores; caregiverassessed
- Observer-Reported Communication Ability Measure (ORCA) Score; caregiver-assessed

Maladaptive Behavior

- Aberrant Behavior Checklist-2 (ABC-2) Scores; caregiver-assessed
- Behavior Problem Inventory-Short Form (BPI-SF) Scores; caregiver-assessed

Sleep: Child Sleep Habits Questionnaire (CSHQ) Scores; caregiver-assessed

GI: Gastrointestinal Health Questionnaire (GIHQ) Scores; caregiver-assessed

Adaptive Behavior: Vineland Adaptive Behavior Scales-3 Scores; clinician-assessed

Motor

o Bayley Scales of Infant Development 4 (BSID-4) motor scale, clinician-assessed (for

participants who are assessed on the BSID-4)

o Modified Two-minute Walk Test scores; clinician-assessed

Quality of Life (Child and Caregiver)

- Quality of Life Inventory-Disability (QI-Disability) Scores; caregiver-assessed
- Impact of Childhood Neurological Disability (ICND) Overall Quality of Life rating; caregiver-assessed

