9. STUDY PROCEDURES

9.1 Overview of Study Visits

The Screening/Baseline period will be conducted over 4 to 6 weeks. The second visit during the Screening/Baseline period (Visit 2) should be conducted 2 weeks \pm 1 day after the Screening visit (Visit 1). The participant will then remain in Screening for an additional 2 to 4 weeks. The caregiver diary must be completed daily during the entire Screening/Baseline period whether it is 4 weeks or 6 weeks. The Screening visit (Visit 1) and Baseline visit (Visit 3) may be conducted over three consecutive days. It is preferrable that ECGs, safety labs and biomarker sample collection are conducted on the same day. No assessments can be conducted until informed consent has been given by the caregiver or legally authorized representative. Also, training for the caregivers on all caregiver completed assessments must be completed before the caregiver rater may complete the assessments. All assessments must be completed within the window for the visit, as shown in the Schedule of Assessments in Section 4. For Visit 3, all assessments must be completed before administration of the IMP.

The in-clinic visits will be conducted in person at the study site. As described below, safety and efficacy assessments will be completed by site personnel. The caregiver will also complete caregiver assessments the day of the visit or the day before the visit as described below (except the caregiver diary which is completed daily), and these will be reviewed by site personnel. In-clinic visits will be done at Screening (Visit 1), Baseline (Visit 3), Week 2 (Visit 5), Week 6 (Visit 9), and Week 13 (EOT, Visit 16). For all visits designated as in-clinic (Visits 1, 3, 5, 9 and 16), an in-person visit is preferred. Off-site assessments may be allowed due to extenuating circumstances due to the COVID-19 health emergency. All requests for off-site assessments must be approved in advance by the Sponsor or Medical Monitor.

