9.4.2 Investigational Medicinal Product Administration

NNZ-2591 Oral Solution, 50 mg/mL will be administered open-label at a target dose of 12 mg/kg BID. The total administration period for NNZ-2591 will be 13 weeks. Participants will be up-titrated to the target dose according to the dosing schedule outlined in Section 7.2. The dose titration schedule may be modified based on updated PK modelling including data from the study.

NNZ-2591 Oral Solution, 50 mg/mL, is provided as a ready-to-use strawberry-flavored liquid for oral administration. The IMP should not be mixed with water, liquid thickeners, or food for administration.

Each day there will be two dose administrations, one in morning and one in afternoon or evening. There should be at least 8 hours between doses. Doses should be given on an empty stomach (2 hours after the previous meal or snack and 30 minutes prior to the next). Doses may be taken over a 10-minute period with a follow up of 250 mL of water.

For all participants, the total duration of NNZ-2591 treatment will be 91 days. Dosing at the end of Baseline counts as Day 1 whether one or two doses are given. Dosing may not exceed 91 days including Day 1, and all efficacy assessments for the EOT visit must be completed on or before Day 91 of treatment.

The first dose of IMP will be administered in the clinic after all Baseline assessments are completed or, if the Investigator judges that it is too late in the day, on the following day. The participant should be monitored for at least three hours after the first dose. If the first dose is administered the day following Baseline, vital signs (except height) should be collected before the dose is administered. Day 1 of dosing is defined by the date when the first dose is taken. At this visit, the site will provide IMP for the caregiver to dispense at home. Enough IMP will be provided to cover the interval until the next in-clinic visit when the caregiver will be re-supplied from site.

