The BSID-4 will be performed at Screening (Visit 1) and End of Treatment (Week 13, Visit 16) on those subjects who cannot be assessed using the SB5. It assesses cognitive ability, motor skills, and behavior and provides standardized scores in five domains: Cognitive (COG), Language (LANG), Motor (MOT), Social-Emotional (SOEM), and Adaptive Behavior. The Adaptive Behavior scale was not collected for this study. Domain scores range from 40 - 160, where higher scores indicate greater ability in the domain area of development. Scaled scores, age equivalents and growth scale values (GSVs) can also be calculated for the scale subtests: cognition (CG), receptive communication (RC), expressive communication (EC), fine motor (FM), and gross motor (GM). Scaled scores and age equivalents can be calculated for the social emotional (SE) subtest. Scale subtest scores range from 1 - 19 with a mean of 10 and SD of 3. Age equivalent scores range from < 0:15 - >41:08, Growth scale scores range from 414 -559 with a mean of 500 and SD of 25. Higher scores indicate greater development in the scale subtest. Raw scores, age equivalent scores and GSV are collected for all subjects. Standard scores and scaled scores are only calculated for participants 42 months and younger.

As part of the analysis, an overall developmental quotient, a verbal developmental quotient, and a non-verbal developmental quotient will also be calculated. These developmental quotients will only be calculated if the contributing scale scores are all non-missing. The developmental quotients will be derived as follows:

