**Overall Developmental Quotient:** 

(Mean of the age-equivalent scores in months of the cognition, fine motor, receptive communication, expressive communications scales/chronological age in months) x 100

Verbal Developmental Quotient:

(Mean of the age-equivalent scores in months of the expressive communication and receptive scales/chronological age in months) x 100

Non-verbal Developmental Quotient:

(Mean of the age-equivalent scores in months of the cognition and fine motor scales/chronological age in months) x 100

Subtest/Subdomain Developmental Quotients:

The developmental quotients for the BSID subtests will be derived. The developmental quotients for each subtest are calculated in a similar manner as the overall, non-verbal, and verbal developmental quotients. Subtest Developmental Quotient = (Age Equivalent Score in Months for the subtest / chronological age in months) x 100.

Chronological age in months will be calculated as (date of assessment – date of birth + 1)/30.4375.

For age equivalent values < 2, the result is entered into EDC as 1.9, for analysis. For age equivalent values > X, where X is a numeric value, the result is entered into EDC as X.1, for analysis. For example, ">33" is entered in EDC as 33.1. The age equivalent score entered into EDC will be converted to months for analysis according to the following algorithm:

- (a) Count the numeric portion of the result before the decimal as months.
- (b) Count (the numeric portion of the result after the decimal multiplied by 10) as days and convert to months by dividing by 30.4375
- Age equivalent score (months) = (a) + (b)

The standard scores have a mean of 100 and a standard deviation of 15. The developmental quotient scores are a ratio of developmental age to chronological age and will have a range of 1 to 100. Higher scores indicate a higher IQ or better developmental progress. If any scores are missing, the subject will be excluded from corresponding summaries.

Within subject change is the difference between the score at EOT and the score at baseline. If a score is missing, that subject will be excluded from the corresponding summaries.

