### 5.2.4 Baseline Values

Baseline values that are missing will not be imputed for safety or efficacy measures. For efficacy assessments scheduled to be collected at more than one visit during the Screening/Baseline period, the baseline value will be based on the average of all nonmissing values from assessments conducted prior to the first dose of study drug. For assessments scheduled to be collected once during the Screening/Baseline period, the value from the most recent non-missing assessment prior to the first dose will be used. For safety and other assessments, the value from the most recent non-missing assessment prior to the first dose will be used.

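### SB5 and BSID-4 scores from up to 3 months before Screening may serve as the baseline for change, which adds up to 3.0 untreated months to the interval tested

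*Protocol*

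**What the plan says.** Protocol 9.5.9.3 schedules the SB5 or BSID-4 at Visit 1 and End of Treatment (EOT) only. If either test was given "within 3 months of Screening, the scores from that administration may be used if it meets the following criteria". The criteria are that site personnel or another study site gave the test, that all required scores are available, and that they may be shared. School and outside-clinic results are barred. No criterion limits reuse to description.

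Protocol 6.3.2.1 introduces the secondary endpoints, which include the BSID-4 motor scale, with "Within-participant changes will be assessed from the Baseline period to End of Treatment (EOT) using the following measures". Protocol 11.3 establishes baseline from assessments made during the Screening/Baseline period, and Protocol 9.1 gives its length: "The Screening/Baseline period will be conducted over 4 to 6 weeks".

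SAP 8.1 lists SB5 and BSID-4 scores among the secondary efficacy variables. For an assessment scheduled once before dosing, SAP 5.2.4 says that "the value from the most recent non-missing assessment prior to the first dose will be used". SAP addendum 9.2.16 repeats the two-point schedule ("The BSID-4 will be performed at Screening (Visit 1) and End of Treatment (Week 13, Visit 16) on those subjects"), defines change ("Within subject change is the difference between the score at EOT and the score at baseline") and applies a Wilcoxon signed rank test to it. SAP addendum 9.2.18 summarises SB5 change in z-deviation, change-sensitive and age-equivalent scores. For the SB5, a test follows only from the general text of SAP 9.2.

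**The concern.** A reused score is harmless for describing the sample or as a covariate. It is different when that score is subtracted from the EOT value. The change then spans time before Screening, the run-in and the treatment period, and only the last is on drug. Ordinary development over the extra time raises scores that are not age-normed. A single-arm test against zero cannot separate that rise from a drug effect.

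Reuse also departs from the plan's own definition of change from the Baseline period, and it pools children whose change scores cover very different intervals. SAP 6.3 has rules for partial or duplicate SB5 and BSID-4 scores but none for reused ones. Neither document plans a flag, an interval adjustment or a sensitivity analysis.

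**Working it through.** The documents give no figure for this interval, so there is none to reproduce.

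**Inputs**
- Reuse allowance: 3 months (Protocol 9.5.9.3). At the SAP's 30.4375 days per month this is 91.3 days, taken as 91.
- Run-in from Visit 1 to first dose: 4 to 6 weeks, or 28 to 42 days (Protocol 9.1).
- Treatment: "Dosing may not exceed 91 days including Day 1" (Protocol 9.4.2). Day 1 to Day 91 is 90 elapsed days and 91 dosing days.

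**Intervals.** Untreated time = reuse + run-in. Interval = untreated time + 90. On-drug share = 91 / interval.

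| Baseline | Run-in (days) | Untreated before first dose | Baseline to Day 91 | On-drug share |
|---|---|---|---|---|
| Visit 1 | 28 | 28 days (0.9 months) | 118 days | 91/118 = 77.1% |
| Visit 1 | 42 | 42 days (1.4 months) | 132 days | 91/132 = 68.9% |
| Reused, at limit | 28 | 119 days (3.9 months) | 209 days | 91/209 = 43.5% |
| Reused, at limit | 42 | 133 days (4.4 months) | 223 days | 91/223 = 40.8% |

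Counting 91 rather than 90 elapsed days moves these shares by less than one percentage point. Of the 4.4-month maximum, reuse contributes 3.0 months. The other 1.4 months is the ordinary run-in.

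**Effect on scores that rise with development.** At any constant rate, non-drug gain is proportional to the interval. At the reuse limit it is larger by a factor of 209/118 = 1.77 or 223/132 = 1.69, that is, by 69–77%. In absolute terms, with an assumed untreated rate of 0.1 to 0.3 age-equivalent months per month:
- from reuse alone: 0.1 × 3.0 = 0.3 to 0.3 × 3.0 = 0.9 months;
- from a 6-week run-in, present without reuse: 0.1 × 1.38 = 0.14 to 0.3 × 1.38 = 0.41 months.

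**Effect on the developmental quotient (DQ).** SAP addendum 9.2.16 divides age equivalent by age at the assessment date. If development continues at the child's prior average rate r, then age equivalent = r × age at both times and DQ stays at 100r over any interval, so the bias is zero. If development slows, DQ falls. For example, take DQ 20 at 60 months (age equivalent 12) and a gain of 0.1 per month over 7.3 months: (12 + 0.73) / (60 + 7.3) × 100 = 18.9. If development speeds up, DQ rises.

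**The case against.** The strongest reply is that little rests on these analyses. SAP 9.1 has no primary efficacy endpoint, SAP 5 calls the tests descriptive, SAP 8.5 says no formal analysis is planned, and maturation affects every change score in an uncontrolled study. This stands as a limit on the harm. It does not justify a baseline rule that adds up to three further months for some children on one pair of instruments and not for others.

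Second, the size is unknown. The documents give no untreated growth rate, and Protocol 6.2.2 describes people who stay at low functional levels as they age. Hence the range rather than a single value. Exclusion 37 bars persistent skill loss within 3 months of Screening, which makes an offsetting decline over the reuse window less likely.

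Third, it is not known that any child is affected. SAP 2.2 says nobody was enrolled under protocol version 3.0, the version reviewed here, and the version 2.2 schedule reproduced in the SAP mentions no reuse. Whether earlier versions allowed it cannot be checked. The current protocol does allow it, and SAP 5.2.4 has no safeguard against it.

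Fourth, repeat testing may bring a practice gain, and Protocol 8.5 names fatigue and frustration as risks of assessment. The burden is real but limited to a test that Table 1 already schedules. A practice gain from the earlier test would enter the Visit 1 baseline, so it would not inflate the later change.

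**Conclusion.** The point holds as a gap in the baseline rule. At the limit, reuse lengthens untreated time from 28–42 days to 119–133 days and cuts the on-drug share of the interval from 69–77% to 41–44%. That can inflate BSID-4 raw, age-equivalent and growth-scale gains and SB5 change-sensitive and age-equivalent gains. The 0.3 to 0.9 age-equivalent months due to reuse depends wholly on the assumed rate, and it is a ceiling for a child tested a full three months early.

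A reader might infer more than the documents support:
- That reuse causes all 4.4 months. Up to 1.4 months of it applies to every child because the test is given at Visit 1.
- That quotients are biased downward. DQ is unbiased at a constant prior rate. Otherwise both DQ and z-deviation scores, which use age at assessment, could move either way.
- That a few reused scores would change a signed-rank result. This cannot be judged without the number of such scores and a growth rate.

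**What to change.** In Protocol 9.5.9.3, limit reused scores to baseline description and the nonverbal IQ/DQ covariate, and give the test at Visit 1 as Table 1 schedules. In SAP 5.2.4, 9.2.16 and 9.2.18, define baseline for SB5 and BSID-4 change as an assessment done between consent and first dose.

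If data are already collected, so that retesting is no longer possible, flag reused scores by actual test date. Exclude them from the SB5 and BSID-4 change summaries and tests, and show results with and without them.

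The cost is a short protocol edit and a few lines of SAP text. A few children would repeat a test or leave one secondary analysis, which matters somewhat in a study of 10 to 20. If no scores were reused, the SAP change alters no result. The 28 to 42 untreated days between Visit 1 and first dose remain and should be stated when the change scores are reported.
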